6.4.2.2 Safety variables

AEs

All AEs will be classified by system organ class and by preferred term using MedDRA and those occurred at baseline and after administration of the investigational products will be

summarised in separate lists. AEs occurred after administration of the investigational products will be classified by system organ class and by preferred term using MedDRA independently for each treatment group. Data on drug-related AEs will be collected in the same manner, as required. The number of subjects who developed AEs, drug-related AEs, SAEs, and AEs led to withdrawal from the study will be summarised for each treatment group, together with the total number of AEs, drug-related AEs, SAEs and AEs leading to withdrawal from the study.

Clinical laboratory values

Quantitative data of clinical laboratory values will be summarised using descriptive statistics and qualitative data will be summarised using frequency table for each treatment group at each timepoint.

Vital signs

Quantitative data of vital signs will be summarised for each treatment group at each timepoint using descriptive statistics.

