- The proportion of subjects without each GERD symptom or with ‘Mild’ GERD symptoms up to 1 day during the 7 days preceding visit at Week 1, 2, 4 and 8.

[Patient reported outcomes (PROs)]

- QOLRAD

– Safety

- AEs
- Laboratory test values
- Vital signs (blood pressure, pulse rate)

Statistical methods

The healing rate of RE at Week 8 and its two-sided 95% confidence interval will be calculated for each group. The difference in healing rates between the D40 group and O20 group (D40 group – O20 group) and that between the D20 group and O20 group (D20 group – O20 group) as well as respective two-sided 95% confidence intervals will be obtained. It is concluded that the non-inferiority of D40 to O20 is verified if the lower limit of the two-sided 95% confidence interval of the difference between D40 group and O20 group exceeds -10%. If the non-inferiority of D40 to O20 is verified, verification of the non-inferiority of D20 to O20 will be investigated similarly. The healing rates at Week 8 will be compared between D40 group and O20 group and between D20 group and O20 group using Cochran-Mantel-Haenszel test

stratified by the baseline LA classification or CYP2C19 genotype. In these comparisons, the significant level will not be adjusted.

For safety variables, quantitative data will be summarised for each treatment group using descriptive statistics and qualitative data will be summarised for each treatment group using a frequency table.

TABLE OF CONTENTS	PAGE
TITLE PAGE	1
PROTOCOL SYNOPSIS.....	2
TABLE OF CONTENTS.....	6
LIST OF ABBREVIATIONS AND DEFINITION OF TERMS	11
1. INTRODUCTION	13
1.1 Background	13
1.2 Rationale	15
2. STUDY OBJECTIVES.....	16
2.1 Primary objective	16
2.2 Secondary objectives	16
3. STUDY PLAN AND PROCEDURES	16
3.1 Overall study design and flow chart	16
3.2 Rationale and risk/benefit assessment.....	19
3.2.1 Rationale for study design, doses and control groups.....	19
3.2.2 Risk/benefit and ethical assessment.....	20
3.3 Selection of study population.....	21
3.3.1 Study selection record.....	21
3.3.2 Inclusion criteria	21
3.3.3 Exclusion criteria	21
3.3.4 Restrictions	24
3.3.5 Discontinuation of subjects from treatment or assessment.....	24
3.3.5.1 Criteria for discontinuation	24
3.3.5.2 Procedures for discontinuation	25
3.4 Treatments.....	25
3.4.1 Identity of investigational products.....	25
3.4.2 Doses and treatment regimens	26
3.4.3 Labeling	27
3.4.4 Storage	27
3.4.5 Accountability.....	27

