3. STUDY PLAN AND PROCEDURES

3.1 Overall study design and flow chart

This Clinical Study Protocol has been subjected to a peer review according to AstraZeneca standard procedures.

This is a multicentre, randomised, double-blind, double dummy, parallel-three group study to evaluate the efficacy and safety of D20, D40 and O20 in patients with RE.

The subjects with RE endoscopically verified grade A, B, C or D by LA classification at the time of screening, that is, within 1 week prior to initiation of the investigational product administration, will be classified based on the LA classification in grade A/B and C/D, and will be randomised to D20 group, D40 group or O20 group at the ratio of 1:1:1 in each group.

Esophagogastroduodenoscopy (EGD) will be done at Week 4 and 8 to find whether RE is healed or not. If the healing is observed at Week 4 in a subject, the subject will complete the study at the time point. The maximum duration of investigational product administration

period is 8 weeks. In addition to checking the safety throughout the study period (from the day of informed consent to the day of the last scheduled visit or withdrawal), the GERD symptoms are assessed by subjects themselves using the patient diary. Furthermore, HRQOL is assessed using QOLRAD.

A patient whose RE is healed in this study may be enrolled in the follow-on clinical study (D961HC00006) in which the efficacy and safety of D961H will be assessed on the maintenance of healed RE after the informed consent and the eligibility assessment.

All EGD images of all patients allocated the investigational products during the study period will be reviewed by the central evaluation committee (see Section 6.7) established by AstraZeneca K.K. under the blinded conditions as needed.

Figure 1 and Table 1 present the study flow chart and the schedule of the study.

Figure 1 Study flow chart

[figure not shown]

Table 1 Study plan

	Screening		Study Treatment	
		Randomisation		
Visit	1	2	3 Week 4	4 (or at discontinuation) Week 8
Days after Visit 2	-7 to 0	0	28	56
Time window (days)	-	-	±4	±4
Informed consent ¹⁾	X			
Inclusion/exclusion criteria	X	X		
Demographic data	X			
Medical/surgical history	X			
Underlying diseases	X	X		
Physical examination	X	X	X	X
Vital signs	X		X	X
Clinical laboratory tests ²⁾	X		X	X
Pregnancy test (urine) ³⁾	X			
Hp test (IgG antibody)	X ⁶⁾			
Genetic test for CYP2C19	X ⁶⁾			
QOLRAD (HRQOL)		X	X ⁸⁾	X ⁸⁾
EGD ⁴⁾	X ⁷⁾		X ⁹⁾	X
Randomisation		X		

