Dispense Patient Diary		X	X	
Review/Collect Patient Diary			X	X
Dispense investigational products		X	X	
Review/Collect returned investigational products			X	X
Review treatment compliance			X	X
Check concomitant medications	←			→
AEs ⁵⁾	←			→

1) Within 3 weeks (21 days) before visit 2 (randomisation).

2) Central laboratory is used for laboratory tests. If the results of test conducted within 2 weeks before randomisation at the laboratory test department of each participating medical institution are available, the

eligibility may be checked using these test values even if obtained before the informed consent. However, the baseline laboratory test values should be determined within 1 week before randomisation at the central laboratory.

- 3) Conducted in pre-menopausal females with a child-bearing potential.
- 4) Conducted in fasting condition.
- 5) As to serious adverse events (SAEs) and AEs resulting in discontinuation, all those that occur after informed consent are recorded in the electronic case report form (eCRF). As to the AEs other than serious or resulting in discontinuation, those that occur from the start of investigational product administration to the day of the last scheduled visit or withdrawal are recorded in eCRF.
- 6) If it is not possible to conduct it at the time of screening, the test may be conducted at any visit during the treatment period until the discontinuation or completion of this study.
- 7) If the results of test conducted within 1 week before randomisation are available, these data may be used with the consent of subject even if obtained before informed consent.
- 8) The subject fills in QOLRAD after receiving EGD.
- 9) When the healing of RE is verified by EGD, this study is completed.

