3.4.2 Doses and treatment regimens

One D961H capsule and 2 omeprazole tablets will be orally administered once daily after breakfast for 4 weeks or 8 weeks. However, on the days of dispensing the investigational products, patients must be instructed to take the investigational products at any time on the same day. On the days when EGD are conducted (Visits 3 and 4), patients must be instructed to take the investigational products after the completion of the tests.

Table 3 shows combination of the investigational products for each group.

Table 3 **Combination of investigational products**

	D40	D20	O20
D961H capsule 40 mg	1 capsule	-	-
D961H capsule 20 mg	-	1 capsule	-
D961H capsule placebo	-	-	1 capsule

Table 3 **Combination of investigational products**

	D40	D20	O20
Omeprazole tablet 10 mg	-	-	2 tablets
Omeprazole tablet placebo	2 tablets	2 tablets	-

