4.6.1.2 Method of assessment

When no breaks in the esophageal mucosa are found by EGD, the RE will be judged as "healed". When healing of RE is verified on Visit 3, the subject will complete the study at the time point.

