4.7.1.2 Recording of AEs

For AEs spontaneously reported by the subject and/or in response to an open question “Have you had any health problems since the previous visit/during the study period?” asked by the investigator(s) or revealed by observation, only those occurring from initial administration to the last scheduled visit or withdrawal will be recorded at each visit.

Of SAEs and AEs leading to discontinuation of the subject from the study, those occurring during the time from informed consent to the last scheduled visit or withdrawal will be recorded at each visit.

In case any AE occurs, details (such as a description of the event, seriousness, maximum intensity, date of onset, date of resolution, outcome, action taken [investigational products], and causality with the investigational products) should be recorded in the eCRF.

(a) Abnormal findings

The investigator(s) will confirm whether clinically important values and changes from baseline on clinical laboratory or vital signs are observed or not. If any, such findings will be recorded in the specified module of eCRFs. However, if the abnormality meets any of the following criteria, the abnormality should be recorded in eCRF as AE:

- The abnormality results in discontinuation of the study.
- The abnormality meets any criterion for SAE.
- Investigator(s) insists it should be reported as an AE.

If the abnormality is associated with clinical signs and symptoms, the sign/symptom should be recorded in eCRF as AE.

If any abnormal laboratory values and vital signs considered as clinically important values or changes were observed at the time of completion or discontinuation of the study treatment, the investigator(s) will perform additional tests and follow-up until they are recovered or until the investigator(s) consider it is not necessary to be followed. However, there is no need to record the test results in the eCRF. The monitor will record the follow-up results on the monitoring visit report.

(b) EGD findings of disease under the study (RE)

The EGD findings of RE are not reported as the AEs except for those that correspond to the SAE definition (see Section 4.7.1.1), or those whose aggravation resulted in discontinuation of study.

(c) Assessment of causality

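### Crude AE counts describe risk per treat-until-healed course and understate risk per unit of exposure in a faster-healing arm, by 0 to about 5 percentage points under assumed rates

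*Protocol*

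**What the plan says.** **AE summary.** Section 6.4.2.2 classifies AEs by system organ class and preferred term per arm. It then gives the number of subjects with AEs, drug-related AEs, SAEs and AEs leading to withdrawal, plus the event totals: "SAEs, and AEs led to withdrawal from the study will be summarised for each treatment group, together with the total number of AEs". For safety data of this kind the synopsis says: "qualitative data will be summarised for each treatment group using a frequency table". Neither place mentions person-time, time to event or a split by period.

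**When a subject stops.** Section 3.1: "If the healing is observed at Week 4 in a subject, the subject will complete the study at the time point". Section 4.6.1.2 and footnote 9 of Table 1 repeat the rule ("When the healing of RE is verified by EGD, this study is completed"). Under section 3.4.2 the products are "orally administered once daily after breakfast for 4 weeks or 8 weeks".

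**When AE recording stops.** For AEs in general, section 4.7.1.2 says "only those occurring from initial administration to the last scheduled visit or withdrawal will be recorded at each visit", and footnote 5 of Table 1 agrees. For SAEs and AEs leading to discontinuation, recording starts at consent but ends at the same point. AEs unresolved at that point are followed up, but no later window collects new ones.

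**The concern.** Length of observation is set by an efficacy result obtained after randomisation. If Week 4 healing differs between arms, the arms are watched for different average times. With the same AE hazard everywhere, the faster-healing arm then shows fewer subjects with AEs and fewer AEs.

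A secondary objective is to evaluate the safety and tolerability of all three arms, and tables set side by side will be read as comparative tolerability. Section 1.1 reports that D40 healed more patients than omeprazole 20 mg at both 4 and 8 weeks overseas. If that recurs here, the higher dose would be the arm observed for less time.

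Laboratory and vital-sign summaries have a related feature. Visit 4 takes place only in subjects not healed at Week 4 (its column in Table 1 also serves discontinuation visits), so Week 8 values come from a group selected by response.

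**Working it through.** The protocol states no AE rate, Week 4 healing rate or exposure figure, so there is no figure of its own to reproduce.

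**Inputs from the protocol:** 4 or 8 weeks of treatment and observation; 185 subjects per arm (section 6.5).

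**Assumptions:** share healed at Week 4 (h) of 50% to 80%; AE incidence if everyone were observed for 8 weeks (r8) of 20%, 40% or 60%; constant hazard, equal in both arms; dropout and the ±4-day visit window ignored.

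**Formulas**
- Mean weeks observed = 4h + 8(1 − h).
- Weekly hazard L = −ln(1 − r8)/8.
- Crude incidence = h(1 − e^(−4L)) + (1 − h)(1 − e^(−8L)).
- Difference between arms with healing h0 < h1 = (h1 − h0)(e^(−4L) − e^(−8L)).

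**Worked case: 60% vs 70%, r8 = 40%.** Mean time is 5.6 vs 5.2 weeks. For 185 subjects this is 185 × 5.6/52.18 = 19.9 vs 185 × 5.2/52.18 = 18.4 patient-years, 7% less. Here e^(−8L) = 0.600 and e^(−4L) = √0.600 = 0.775. Crude incidence is 29.5% vs 27.8%, and the difference is 0.10 × 0.175 = 1.7 points.

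| Week 4 healing, slower vs faster | Mean weeks | Event-count ratio | Incidence lower by (points), r8 = 20 / 40 / 60% |
|---|---|---|---|
| 60% vs 60% | 5.6 vs 5.6 | 1.00 | 0 / 0 / 0 |
| 60% vs 65% | 5.6 vs 5.4 | 0.96 | 0.5 / 0.9 / 1.2 |
| 60% vs 70% | 5.6 vs 5.2 | 0.93 | 0.9 / 1.7 / 2.3 |
| 60% vs 80% | 5.6 vs 4.8 | 0.86 | 1.9 / 3.5 / 4.6 |
| 50% vs 70% | 6.0 vs 5.2 | 0.87 | 1.9 / 3.5 / 4.6 |

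**Upper bound.** Write x = e^(−4L). Then e^(−4L) − e^(−8L) = x − x², which is at most 0.25. Under a constant hazard, a 20-point healing gap cannot shift crude incidence by more than 0.20 × 0.25 = 5 points.

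**What excess this could offset.** Take 60% vs 80% with r8 = 40%, so L = 0.0639 and the slower arm shows 29.5%. The faster arm shows the same figure when 0.8x + 0.2x² = 0.7048. This gives x = 0.743 and a hazard of −ln(0.743)/4 = 0.0743 per week, a hazard ratio of 0.0743/0.0639 = 1.16. For 60% vs 70% the same calculation gives 1.08.

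**If AEs cluster early.** Let the rate in Weeks 5–8 be half that in Weeks 1–4, with 60% vs 70% healed. Relative event counts are 4 + 0.5 × 1.6 = 4.8 and 4 + 0.5 × 1.2 = 4.6, a ratio of 0.96 instead of 0.93. The exposure-adjusted rates are 4.8/5.6 = 0.857 and 4.6/5.2 = 0.885, a ratio of 1.03. Exposure adjustment then tilts slightly the other way, whereas a comparison limited to Weeks 0–4 stays at 1.00.

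**The case against.** **The detail belongs in the SAP.** Section 6.1 defers to a comprehensive SAP, which is not at hand, and section 6.4.2.2 excludes nothing. This stands in part: a reader should not infer that the protocol rules out exposure-adjusted rates. But it does not leave the measure open. It specifies counts, and these fit a response-dependent follow-up badly.

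**Crude incidence is legitimate, and safety is descriptive.** The healing and symptom objectives are worded as comparisons with O20; the safety objective is not, and no between-arm AE test is planned. This stands. Counts are a valid summary of risk per course, but the protocol does not say that this is what they represent.

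**A large Week 4 gap has no source.** This stands. Section 1.1 gives only a direction at Week 4, for D40 against omeprazole. Section 3.2.1 reports no Week 8 difference in grades A and B, which section 3.5 allows to be about 455 of 555 subjects (82%). The planning gap for D20 against O20 at Week 8 is 3 points (section 6.5).

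**The shift lies inside sampling error.** At 34% incidence, the 95% half-width of a difference is 1.96 × √(2 × 0.34 × 0.66/185), about 9.7 points. This is true, and no decision rule depends on the AE table. The shift is nevertheless systematic and its direction can be known.

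**Laboratory tests and vital signs are partly covered.** Both are scheduled at Visit 3, before healed subjects leave, and are summarised at each timepoint. Week 4 therefore already gives a comparison that is not selected on healing.

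**Conclusion.** The point holds in a limited form. Crude counts per arm measure AE risk over a treat-until-healed course. They understate risk per unit of exposure in any arm that heals faster by Week 4, provided AEs can occur in Weeks 5–8. The size is 0 to about 5 percentage points, with Week 4 healing gaps of 0 to 20 points, 8-week AE incidence of 20% to 60% and a constant hazard. It is zero if Week 4 healing is equal and smaller if AEs come early.

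A reader might infer that a real dose-related AE excess would be masked. The figures do not support that: the distortion can attenuate an excess with a hazard ratio of roughly 1.1 to 1.2, not hide a large one. Nor do the documents establish that Week 4 healing will differ by any particular amount between the three arms.

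**What to change.** Keep the crude tables and state that they describe events per treat-until-healed course. Add to section 6.4.2.2:

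1. An AE table by arm restricted to onset up to Visit 3, where planned observation is the same in all arms. This should be the main between-arm display.
2. Total exposure and exposure-adjusted AE rates by arm for the full period.
3. For laboratory values and vital signs, use the Week 4 summary for reading across arms, and label Week 8 values as coming only from subjects unhealed at Week 4. A last on-treatment value summary is optional.

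The cost is a few extra tables. Section 4.7.1.2 already has AE onset dates recorded, and dosing and visit data are collected, so no new data and no change to treatment or stopping are needed. There are two limits. The Visit 3 table leaves out events in Weeks 5–8, which the second display covers. Exposure-adjusted rates assume a roughly constant hazard, which is why they should support the Visit 3 table and not replace it.

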6.5 Determination of sample size

There are two criteria that are used to determine the sample size for this study.

One is the statistical power to show the non-inferiority of D20 to O20 in healing of RE at Week 8. The other is the probability of obtaining that the observed healing rate of D20 is lower than that of O20 under an assumption that the true healing rate of D20 is higher than that of O20.

The non-inferiority will be concluded when the lower limit of two-sided 95% confidence interval of the difference of healing rates at Week 8 between D20 and O20 is higher than or equal to -10%. Based on the results of the overseas studies (SH-QBE-0013/172, SH-QBE-0016/173, SH-QBE-0017/174, SH-QBE-0052/222), 172 patients per treatment group are required to keep a 90% power or more with the lower limit of two-sided 95% confidence interval of the difference to be greater than or equal to -10% under the assumption that the healing rates of RE at Week 8 are 85% for D20 and 82% for O20, respectively.

In order to ensure sufficient “power” for the observed responses to show that the healing rate of D20 is numerically higher than that of O20, it is calculated that 182 patients will be needed for each of these treatment groups to ensure a less than 20% probability that the healing rate of D20 would result in an observed response rate greater than that for O20.

Accordingly, we decided to randomize 185 patients per group in the planned study to fulfil the above two criteria (a total of 555 patients in 3 groups).

6.6 Interim analyses (Not applicable)

6.7 Central evaluation committee

For this study, a central evaluation committee that consists of experts in the gastrointestinal area will be established to confirm the rationale for judgement by the investigator(s) based on the EGD images.

The board will review all EGD images of all patients allocated the investigational products during the study period as needed and report the results of the review to AstraZeneca K.K..

Time to hold the meeting and the responsibilities of the board members will be determined separately.

7. STUDY MANAGEMENT

7.1 Monitoring

Before the first subject is entered into the study, a representative of AstraZeneca will visit the investigational study site to:

- Determine the adequacy of the facilities
- Discuss with the investigator(s) (and study coordinators) their responsibilities with regard to protocol adherence, and the responsibilities of AstraZeneca or its representatives. This will be documented in a Clinical Study Agreement between AstraZeneca and the principal investigator
- Discuss the specific requirements of the genetic test with the investigator(s) (and study coordinators)

During the study, a monitor from AstraZeneca or company representing AstraZeneca will have regular contacts with the study site, including visits to:

- Provide information and support to the investigator(s)
- Confirm that facilities remain acceptable
- Confirm that the investigator(s) and study coordinators are adhering to the protocol, that data are being accurately recorded in the eCRFs, and that investigational product accountability checks are being performed
- Perform source data verification (a comparison of the data in the eCRFs with the subject's medical records at the hospital or practice, and other records relevant to the study). This will require direct access to all original records for each subject (eg, clinic charts).

- Perform source verification of the genetic consent of participating subjects and ensure that the investigational team is adhering to the specific requirements of this genetic test

The monitor or another AstraZeneca representative will be available between visits if the investigator(s) or study coordinators at the centre need information and advice.

Source data are any data generated as a result of the subject's inclusion in the study (including run-in and/or follow up related to the study) and includes all related medical examinations and other records. Original data recorded on the eCRFs and regarded as source data are specified in the Clinical Study Agreement between AstraZeneca and the principal investigator

7.1.1 Direct access to source data in Japan

The head of the study site and the investigator(s) should cooperate for monitoring and audit by AstraZeneca, and accept inspection by the IRB or regulatory authorities. All study documents such as raw data should be open for direct access to source data at the request of the monitor and the auditor representing AstraZeneca, the IRB, or regulatory authorities.

The monitor(s) will verify data from the eCRFs against source data to ensure accuracy and completeness of documentation. When the data in the eCRF are changed or modified, the monitor will confirm the amended part (and the reason for amendment) with the investigator(s).

